3.2 Safety Analysis Population

The safety population includes all randomized patients who receive at least one dose of study drug.

4. SAMPLE SIZE AND POWER CALCULATIONS

No formal sample size estimation was performed. This proof of concept study will include approximately 15 evaluable patients randomized in a 2:2:1 ratio to receive Saroglitazar Magnesium 2 mg (6 patients), Saroglitazar Magnesium 4 mg (6 patients) and placebo (3 patients).

Document Title:	Statistical Analysis Plan		
Version Number:	1.0	Date:	31 Mar 2020
Protocol Number:	SARO.17.004	Sponsor Name:	Zydus Discovery DMCC

5. PATIENT CHARACTERISTICS AND STUDY CONDUCT SUMMARIES

Disposition of Patients

Patient disposition table will be based on all enrolled subjects who are consented to participate in the study. The following summaries will be included in the disposition table: total number of subjects screened in the study, number of subjects who failed screening, number of subjects randomized, number of subjects who completed the study, and number and percentage of subjects who discontinued from the study with reason for discontinuation. Percentages will be based on the number of subjects who are randomized. In addition, the number of subjects included in each analysis population (mITT, PP and Safety) will be presented separately.

Demographic and Baseline Characteristics

Demographic and baseline characteristics will be summarized based on the mITT, PP and Safety populations.

Descriptive summaries will be provided for the demographic and baseline characteristics. Demographic characteristics such as age, gender, race, ethnicity, height, weight and Body Mass Index (BMI) will be summarized and tabulated for all the analysis populations. All the continuous variables (i.e., age, height etc.) will be summarized by n, mean, standard deviation, minimum, median and maximum values. All the categorical variables (i.e., gender) will be summarized as count and percentage. All demographic and baseline characteristics will be presented in data listings.

Medical history, previous and concomitant therapies

Medical history information will be coded using the Medical Dictionary for Regulatory Activities (MedDRA[®], version 21.0 or higher). A summary will be provided including the frequency and percentage of subject with medical history terms by System Organ Class and Preferred Term for the Safety population. A by-subject listing of medical history information will be provided for all enrolled subjects including current and past diseases.

Prior therapies are the therapies/medications with stop date prior to first dose of study drug. Any therapy/medication usage at or post first dose of study drug is considered concomitant therapy.

All medications recorded during the study will be coded using the World Health Organization (WHO) Drug Dictionary (version DDEBSEP16). A summary will be provided for the

Document Title:	Statistical Analysis Plan		
Version Number:	1.0	Date:	31 Mar 2020
Protocol Number:	SARO.17.004	Sponsor Name:	Zydus Discovery DMCC

frequency and percent of subjects who had previous therapies/medications and a separate summary of subjects who had concomitant therapy/medications. Summaries will be based on the Safety population and will be by Anatomical Therapeutic Chemical (ATC) classification level 3 term and Preferred Name.

A listing of all prior and concomitant medications including the reported term, Preferred Name, ATC level 3 term, start dates, stop dates and other relevant data will be provided for all enrolled subjects.

6. EFFICACY ANALYSIS STRATEGY

6.1 General Considerations

Categorical variables will be summarized with the frequency and percentage of subjects in each category. Continuous variables will be summarized descriptively with the number of subjects, mean, standard deviation, minimum, median and maximum values. Change from baseline will be summarized similarly, but also with standard error. The change from baseline will be calculated as follows:

Change from baseline = Post baseline value – Baseline value

Percent Change = (Post baseline value – Baseline value) / Baseline value * 100.

The SAS® software (version 9.4) will be used for all analyses.

Decimal Precision

Unless otherwise noted, mean, median, standard deviation, minimum and maximum will be presented to two decimal places, percentage and confidence interval will be presented to one decimal place; and p-values will be presented to four decimal places.

Missing Date Procedures

Adverse events with completely missing dates will be considered treatment emergent. Medications with completely missing end dates will be considered concomitant. Adverse events and medications with partially missing start or end dates will be considered treatment-emergent and concomitant respectively unless the non-missing portion of the dates definitively proves otherwise.

For example, if a subject starts treatment on 20FEB2016, then adverse events with onset dates of FEB2016, 2016, or 05DEC would all be considered treatment-emergent, while

Document Title:	Statistical Analysis Plan		
Version Number:	1.0	Date:	31 Mar 2020
Protocol Number:	SARO.17.004	Sponsor Name:	Zydus Discovery DMCC

onsets dates of 2015 or JAN2016 would not be considered treatment-emergent. Medications starting or ending in FEB2016 or 2016 would be considered concomitant, medications ending in JAN2016 or 2015 would not.

6.2 Efficacy Endpoints

Primary Efficacy Endpoint:

The primary efficacy endpoint is the changes in NAFLD Activity Score (NAS) at Week 24 from baseline with no worsening of fibrosis.

Secondary Efficacy Endpoints:

The secondary efficacy endpoints are:

- Percentage of patients with decrease from baseline in NAFLD activity score by at least 2 point spread across in at least 2 of the NAS components (steatosis, hepatocyte ballooning, and lobular inflammation) at Week 24 with no worsening of fibrosis
- Percentage of patients with disappearance of steatohepatitis at Week 24.
- Change from baseline in stage of steatosis, lobular inflammation and ballooning at Week 24.
- Change from baseline in stage of fibrosis at Week 24.
- Change from baseline in liver function tests parameters (ALT, AST, ALP, GGT, Direct bilirubin, Total proteins and Albumin) at Week 24.
- Change from baseline in lipid profile parameters (TG, TC, sdLDL, HDL, LDL, VLDL, non-HDL, ApoA1 and ApoB) at Week 24.
- Changes from baseline in glycemic control and insulin resistance parameters (FPG, HbA1c, Fasting insulin, C-peptide, Adiponectin, HOMA-B and HOMA-IR) at Week 24.

6.3 Efficacy Hypotheses

This is a proof of concept study and no formal hypothesis testing will be conducted.

6.4 Statistical Methods for Efficacy Analyses

This is a proof of concept study with a small number of patients enrolled. All primary and secondary efficacy endpoints will be summarized descriptively by treatment as per section 6.1 for both mITT and PP populations.

Fisher's exact test will be used to compare the treatment differences for following endpoints in Saroglitazar 2 mg and Saroglitazar 4 mg treatment groups with placebo.

Document Title:	Statistical Analysis Plan		
Version Number:	1.0	Date:	31 Mar 2020
Protocol Number:	SARO.17.004	Sponsor Name:	Zydus Discovery DMCC

- Percentage of patients with decrease from baseline in NAFLD activity score by at least 2 point spread across in at least 2 of the NAS components (steatosis, hepatocyte ballooning, and lobular inflammation) at Week 24 with no worsening of fibrosis.
- Percentage of patients with disappearance of steatohepatitis at Week 24.

Disappearance of steatohepatitis is defined as:

- resolution of steatohepatitis on overall histopathological reading and no worsening of liver fibrosis on NASH CRN fibrosis score (or)
- improvement in liver fibrosis greater than or equal to one stage (NASH CRN fibrosis score) and no worsening of steatohepatitis (defined as no increase in NAS for ballooning, inflammation, or steatosis).

Resolution of steatohepatitis is defined as absent fatty liver disease or isolated or simple steatosis without steatohepatitis and a NAS score of 0–1 for inflammation, 0 for ballooning, and any value for Steatosis.

Two-sample t-test will be used to compare the treatment differences for the following endpoints in Saroglitazar 2 mg and Saroglitazar 4 mg treatment groups with placebo.

- Change from baseline in stage of steatosis, lobular inflammation and ballooning at Week 24.
- Change from baseline in stage of fibrosis at Week 24.
- Change from baseline in liver function tests parameters (ALT, AST, ALP, GGT, Direct bilirubin, Total proteins and Albumin) at Week 24.
- Change from baseline in lipid profile parameters (TG, TC, sdLDL, HDL, LDL, VLDL, non-HDL, ApoA1 and ApoB) at Week 24.
- Changes from baseline in glycemic control and insulin resistance parameters (FPG, HbA1c, Fasting insulin, C-peptide, Adiponectin, HOMA-B and HOMA-IR) at Week 24.

In addition to the descriptive summaries, treatment differences and 95% confidence for the treatment differences will be provided. All p-values presented are for the descriptive purpose only.

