##### 4.2 INCLUSION CRITERIA

1. Patients able to provide written informed consent for participation in this trial.
2. Males or females, 18 to 75 years of age, both inclusive.
3. Female must be either of non-child bearing potential (surgically sterilized at least 6 months prior to screening or postmenopausal) or using one or more methods of contraception.
4. Histologic confirmation of NASH without cirrhosis (fibrosis stage 0, 1, 2, or 3) from liver biopsy performed either during the screening period or no more than 6 months prior to the first visit, with a NAS of  $\geq 4$  and a score of at least 1 in each (steatosis scored 0-3, ballooning scored 0-2 and lobular inflammation scored 0-3). If biopsy was performed within 6 months of screening, the slides, biopsy material or block should be available for baseline documentation. Such patients, whose historical biopsy report is available, should not use medications suspected of having an effect on NASH for at least 3 months prior to the screening.
5. BMI  $\geq 25$  kg/m^2.

	Approved by: [name] [name]	Protocol No.: SARO.17.004.02.PROTOCOL Version No.: 2.0
---	---	---

 Zydus Discovery DMCC	CLINICAL TRIAL PROTOCOL Saroglitazar Magnesium – Phase 2 SARO.17.004	CONFIDENTIAL Page 28 of 76
--	---	---

6. For hypertensive patients, blood pressure must be controlled by a stable dose of antihypertensive medications for at least 3 months prior to screening (and the stable dose can be maintained throughout the study)
7. Patients with type 2 diabetes mellitus may be included if they fulfil the following criteria;
  - a. Stable therapeutic regimen as defined by no changes in oral agents or dose for at least 3 months before screening and the stable dose can be maintained throughout the study.
  - b. HbA1c  $\leq$  9.5%.
8. Patients agree to comply with the study procedure.

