#### **6.2.2 Secondary endpoints**

From baseline to Week 24:

1. To evaluate the percentage of responders in the treatment groups.

Responder is defined as a decrease from baseline of at least 2 points spread across at least 2 of the NAS components [steatosis, hepatocyte ballooning, and lobular inflammation] with no worsening of fibrosis.

2. Percentage of responders, defined by the disappearance of steatohepatitis.
3. Changes in the stage of steatosis, lobular inflammation and ballooning.
4. Changes in the stage of fibrosis.

	Approved by: [name] [name]	Protocol No.: SARO.17.004.02.PROTOCOL Version No.: 2.0
---	------------------------------------	---

 Zydus Discovery DMCC	CLINICAL TRIAL PROTOCOL Saroglitazar Magnesium – Phase 2 SARO.17.004	CONFIDENTIAL Page 44 of 76
--	---	---

5. Changes in the liver function tests.
6. Changes in the lipid profile.
7. Changes in the glycemic control and insulin resistance.
8. To assess the safety of Saroglitazar Magnesium 2 mg and 4 mg in patients with non-alcoholic steatohepatitis.

(Safety will be assessed during the study period through the reporting of AEs, by clinical laboratory tests, ECGs, vital sign, physical examination and body weight assessment at various time points during the study).

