1. INTRODUCTION

The purpose of this document is to provide a description of the statistical methods and procedures to be implemented for the analysis of data from SARO.17.004 study. This document is based on protocol version 2.0, dated 02 August 2018. The statistical planning and conduct of analysis of the data from this study will follow the principles defined in relevant International Council for Harmonisation (ICH)-E9 guidelines. This Statistical Analysis Plan (SAP) has been developed prior to database lock or final analysis. Any changes from the planned analysis as described in the protocol are detailed here, and any differences described here supersedes the analysis presented in the protocol. Any deviations from the planned analyses described in this SAP will be documented in the clinical study report, together with the reason for such changes.

Prior to start of any statistical analyses, the database must be authorized and all decisions regarding assignment of patients to study populations must be completed. In addition, protocol deviations must be identified prior to the start of statistical analyses.

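### The SAP counts a one-stage fibrosis improvement with unchanged NAS components as 'disappearance of steatohepatitis', so the reported percentage is not a resolution rate

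*SAP*

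**What the plan says.** SAP 6.2 lists among the secondary endpoints "Percentage of patients with disappearance of steatohepatitis at Week 24". SAP 6.4 defines the term by two alternatives. The first limb, with the connector that follows it, is "resolution of steatohepatitis on overall histopathological reading and no worsening of liver fibrosis on NASH CRN fibrosis score (or". The second limb is "improvement in liver fibrosis greater than or equal to one stage (NASH CRN fibrosis score) and no worsening of steatohepatitis", and SAP 6.4 explains that steatohepatitis has not worsened if none of the three NAS components has gone up.

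SAP 6.4 then defines resolution, a term used in the first limb only. Besides the overall reading, it needs "a NAS score of 0–1 for inflammation, 0 for ballooning, and any value for Steatosis".

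Protocol 6.2.2 carries the endpoint as "Percentage of responders, defined by the disappearance of steatohepatitis" and gives no definition. SAP Section 1 states that "any differences described here supersedes the analysis presented in the protocol", so the SAP 6.4 definition is the operative one. Each dose is compared with placebo on this endpoint by Fisher's exact test, with the statement that "All p-values presented are for the descriptive purpose only". Neither document plans to report the two limbs separately.

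**The concern.** The second limb describes a fibrosis outcome. It asks that steatohepatitis be no worse, not that it be gone. Because the limbs are alternatives, a patient whose steatohepatitis is exactly as it was at entry can be reported as one in whom it disappeared.

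What is at stake is the meaning of a reported percentage. A reader will take it as the proportion in whom NASH resolved, but cannot tell from the planned output how many patients met the first limb. The same count feeds the comparison with placebo. The study tests no formal hypothesis, so description is its whole product and the label has to match what is counted.

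**Working it through.** The plan gives no expected rate, power or alpha for this endpoint, so there is no figure of its own to reproduce beyond the allocation: 15 × 2/5 = 6, 15 × 2/5 = 6 and 15 × 1/5 = 3, which agrees with SAP Section 4.

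**Inputs**
- Entry scores (Protocol 4.2): "a score of at least 1 in each (steatosis scored 0-3, ballooning scored 0-2 and lobular inflammation scored 0-3", with total NAS at least 4 and fibrosis stage 0 to 3.
- Limb 1 (SAP 6.4): inflammation 0 or 1, ballooning 0, any steatosis, fibrosis not higher. The pathologist's overall reading is a further condition. It cannot be scored from the components, so leaving it out can only make limb 1 easier to meet.
- Limb 2 (SAP 6.4): fibrosis lower by at least one stage, and no component higher.

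**Step 1: one patient**

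| | Steatosis | Inflammation | Ballooning | NAS | Fibrosis |
|---|---|---|---|---|---|
| Baseline | 2 | 2 | 2 | 6 | 2 |
| Week 24 | 2 | 2 | 2 | 6 | 1 |

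Limb 1 fails, because ballooning is 2 (0 is needed) and inflammation is 2 (at most 1 is allowed). Limb 2 is met. The patient is tabulated as disappearance while still meeting the histological definition of NASH used for entry. The same holds at NAS 8 (3 + 3 + 2) on both occasions with fibrosis going from 2 to 1.

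**Step 2: how general this is**
- Component combinations allowed at entry: 3 × 3 × 2 = 18, less the one with total 3, leaves 17.
- With four fibrosis stages: 17 × 4 = 68 entry profiles.
- Profiles that qualify through limb 2 with all components unchanged: 17 × 3 = 51, that is, every profile at stage 1 to 3. Stage 0 cannot improve.
- Profiles that qualify through limb 1 with all components unchanged: 0 of 68, because entry needs ballooning of at least 1 and resolution needs 0.

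These are counts of possible score profiles, not probabilities.

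**Step 3: direction**

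Every patient who meets limb 1 also meets limb 1 or limb 2. In every arm the composite percentage is therefore at least the limb 1 percentage.

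**Step 4: size per patient**

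One patient counted through limb 2 alone adds 1/6 = 16.7 points in an active arm and 1/3 = 33.3 points on placebo.

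**Step 5: effect on the placebo comparison (two-sided Fisher, hypothetical counts)**

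| Active | Placebo | p |
|---|---|---|
| 4/6 | 0/3 | 21/126 = 0.167 |
| 5/6 | 0/3 | 6/126 = 0.048 |
| 5/6 | 1/3 | 19/84 = 0.226 |

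One extra active patient through limb 2 takes the first row to the second. One extra placebo patient takes the second row to the third. The comparison can move either way.

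**The case against.** The strongest reply is that little hangs on this. The endpoint is secondary, the study is a 15-patient proof of concept without formal testing, the p-values are descriptive, and the composite is prespecified and printed in full. A sponsor may choose such a composite. All of this stands. It limits the weight of the point, but it does not make the label correct, and a printed definition does not let a reader recover the first-limb count.

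The size of the effect is unknown. The documents give no rate of one-stage fibrosis improvement at 24 weeks, and the number of patients counted only through the second limb could be zero. The 51 of 68 follows directly from the rules, and one worked patient is enough to prove the point. In arms this small, one patient moves any binary endpoint by the same amount, and no alpha is set, so crossing 0.05 triggers no decision. These points also stand. The Fisher values show sensitivity, not a bias towards the drug.

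The first limb is not pure resolution either. A patient who resolves but whose fibrosis worsens is left out, so the composite could even be lower than the total number who resolved. That is correct, and it is a reason to label the first limb exactly.

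Finally, table shells are not among the documents and might split the limbs. The component scores and fibrosis stage are also summarised separately. But the SAP text specifies no split, and summaries of change by arm do not show how many individual patients resolved.

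**Conclusion.** The concern holds. As SAP 6.4 is written, the percentage labelled disappearance of steatohepatitis can include patients with no change in any NAS component who fail the SAP's own resolution rule. The direction relative to the first limb is certain: never lower. The size is 16.7 points per such patient in a 6-patient active arm and 33.3 points in the 3-patient placebo arm, assuming the planned arm sizes are reached and all randomised patients are analysed. The number of such patients cannot be estimated from the documents. The effect on the comparison with placebo can go in either direction.

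This should be fixed, but it does not threaten the trial. It concerns the meaning of one descriptive secondary endpoint, not a type I error rate, and the primary endpoint is untouched.

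**What to change.** Amend SAP 6.4 before unblinding, in one of two ways.

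1. Define disappearance of steatohepatitis by the first limb only, and state in the table label that it means resolution without worsening of fibrosis. Report the second limb as a separate, plainly named fibrosis-improvement row. Keep the mITT denominator. The number of patients at baseline stage 1 or higher may be shown beside it, since only they can improve, but should not replace it in arms this small.
2. At minimum, keep the composite under a name that describes both limbs, and tabulate by arm the number meeting the first limb, the second limb only, and either.

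If unblinding has already taken place, report the same split and document it in the clinical study report as a departure from the SAP with its reason, as SAP Section 1 requires.

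The cost is one wording change and one or two table rows, using biopsy scores already collected. Under the first option the disappearance percentage may be lower. Under the second the table is slightly longer.

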## 8.4 DETERMINATION OF SAMPLE SIZE

This proof of concept study will include total 15 patients receiving from a multiple centers in a ratio of 2:2:1 to have 6 patients in Saroglitazar Magnesium 2 mg, 6 patients in Saroglitazar 4 mg and 3 patients in placebo arm for 24 weeks.

	Approved by: [name] [name]	Protocol No.: SARO.17.004.02.PROTOCOL Version No.: 2.0
---	------------------------------------	---

 Zydus Discovery DMCC	CLINICAL TRIAL PROTOCOL Saroglitazar Magnesium – Phase 2 SARO.17.004	CONFIDENTIAL Page 57 of 76
---	---	---

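### For the 23 laboratory endpoints, one three-arm ANCOVA per endpoint would give narrower 95% intervals on average than separate 6 v 3 t-tests on change, if the arms share one variance

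*SAP*

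**What the plan says.** SAP 6.4 sets the method: "Two-sample t-test will be used to compare the treatment differences for the following endpoints in Saroglitazar 2 mg and Saroglitazar 4 mg treatment groups", each against placebo. SAP 6.1 defines the analysed quantity: "Change from baseline = Post baseline value – Baseline value". No model term for baseline is specified, and no variance pooled over the three arms. ANCOVA occurs only in the protocol's abbreviation list.

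The t-test list in SAP 6.4 holds 7 liver, 9 lipid and 7 glycemic or insulin parameters, 23 laboratory endpoints in all. It also holds four ordinal histology stages: fibrosis and the three NAS components, which protocol 4.2 describes as "steatosis scored 0-3, ballooning scored 0-2 and lobular inflammation scored 0-3".

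For the output, SAP 6.4 says "treatment differences and 95% confidence for the treatment differences will be provided" and adds "All p-values presented are for the descriptive purpose only". Protocol 8.4 plans "6 patients in Saroglitazar Magnesium 2 mg, 6 patients in Saroglitazar 4 mg and 3 patients in placebo arm for 24 weeks", and SAP 4 gives the same split of approximately 15 patients.

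**The concern.** With 3 placebo patients, every interval the SAP promises will be wide. The planned test makes them wider than the data require in two ways.

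- Subtracting the baseline fixes its slope at 1. When the baseline/Week 24 correlation is moderate, the change score carries more noise than the residual around a fitted slope, and chance baseline imbalance between 6 and 3 patients is not adjusted for.
- Each contrast estimates its variance from 9 patients, although 15 were measured.

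The study tests no formal hypothesis, so the estimates and their intervals are the result. Their width is therefore the natural yardstick for choosing a method. No decision rule rests on them, so nothing beyond precision is at stake.

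**Working it through.** **Inputs from the documents.** Arms 6/6/3 (SAP 4, protocol 8.4): 15 × 2/5 = 6, 15 × 2/5 = 6, 15 × 1/5 = 3. Endpoints: 7 + 9 + 7 = 23 (SAP 6.4). Interval level 95%. The documents state no SD, effect size or interval width to reproduce.

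**Assumptions.** The documents give no baseline/Week 24 correlation ρ, so 0.3 to 0.9 is used. Data are normal, with the same SD at baseline and Week 24, set to 1. All arms share one variance. The SAP does not say pooled or Welch; the pooled t-test is taken first.

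**Formulas for the mean half-width.** The factor √(1/6 + 1/3) = 0.7071 is common to all three. c4 is the expected value of a sample SD divided by the true SD.

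- Pairwise t-test, 6 + 3 − 2 = 7 df: 2.365 × 0.965 × √(2(1−ρ)) × 0.7071
- Three-arm pooled change, no covariate, 15 − 3 = 12 df: 2.179 × 0.979 × √(2(1−ρ)) × 0.7071
- Three-arm ANCOVA, 15 − 4 = 11 df: 2.201 × 0.978 × √(1−ρ²) × 0.7071 × 1.046

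The 1.046 is the average cost of chance baseline imbalance, E√(1 + F(1,12)/12).

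**At ρ = 0.5.** The t-test gives 2.365 × 0.965 × 1 × 0.7071 = 1.61. ANCOVA gives 2.201 × 0.978 × 0.866 × 0.7071 × 1.046 = 1.38. The ratio is 0.85.

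| ρ | t-test | pooled change | ANCOVA | ANCOVA v t-test | trials where ANCOVA is narrower |
|---|---|---|---|---|---|
| 0.3 | 1.91 | 1.78 | 1.52 | 20% narrower | 80% |
| 0.5 | 1.61 | 1.51 | 1.38 | 15% narrower | 74% |
| 0.7 | 1.25 | 1.17 | 1.14 | 9% narrower | 67% |
| 0.8 | 1.02 | 0.96 | 0.96 | 6% narrower | 64% |
| 0.9 | 0.72 | 0.68 | 0.69 | 4% narrower | 60% |

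The last column is from simulation of 6/6/3 trials (40,000 per case). The simulation also reproduces the widths and gives coverage of 0.95 for all three methods.

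**Where the gain comes from.** Pooling three arms gives (2.179 × 0.979)/(2.365 × 0.965) = 0.935, or 6.5%, at every ρ. The covariate then adds 15% at ρ 0.3, 9% at 0.5 and 3% at 0.7, adds nothing at 0.8, and costs 3% at 0.9.

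**When the common variance fails.** The table multiplies the other dose arm's residual SD, at ρ = 0.5. The pairwise t-test covers 0.95 in every row.

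| SD multiplier | ANCOVA width / t-test width | ANCOVA coverage |
|---|---|---|
| 0.5 | 0.70 | 0.90 |
| 0.75 | 0.77 | 0.93 |
| 1.25 | 0.95 | 0.97 |
| 1.5 | 1.05 | 0.98 |
| 2 | 1.27 | 0.99 |

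The average gain vanishes at an SD ratio of 1.56 (ρ 0.3), 1.38 (0.5), 1.23 (0.7), 1.16 (0.8) and about 1.10 (0.9). With the SD doubled at ρ 0.9, ANCOVA intervals are 43% wider. If placebo has twice the SD at ρ 0.5, coverage is 0.85 for ANCOVA, 0.89 for the pooled t-test and about 0.93 to 0.94 for Welch.

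**The case against.** The strongest reply is that this is a preference between valid methods. The t-test keeps its coverage, the endpoints are secondary, the p-values are descriptive and the sample size depends on none of it. That stands, and it limits how much the point matters.

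The gain also depends on an unknown ρ. The plan asks for stable medication and lifestyle, which arguably favours a high ρ. At 0.8 and 0.9 the SD of the estimate is the same for both methods (0.45 and 0.32), so the shorter interval comes only from the extra df. Three-arm pooling without a covariate then does as well or slightly better. This stands too: the case for the covariate is good at low and moderate ρ and absent from about 0.8 upward.

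ANCOVA makes assumptions that the pairwise test does not: that the other dose arm shares the variance, which cannot usefully be checked with 3 placebo patients, and that the baseline slope is common. Losses concentrated in the other dose arm can also reverse the gain at high ρ: with 3 patients left there and 6 v 3 compared, the width ratio is 1.02 at ρ 0.9. These are reasons to keep the pairwise test as a check.

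Two smaller points. The SAP says approximately 15, so 6 v 3 is the plan and not a strict ceiling. The 7 df presumes the pooled test; against Welch the gain is larger, with a width ratio of 0.66 at ρ 0.3 and 0.80 at 0.9.

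**Conclusion.** The concern holds, as a suggestion to consider. Under a common variance and the planned 6/6/3, three-arm ANCOVA gives a smaller mean 95% interval than the pairwise t-test at every assumed ρ, by 20% at 0.3 falling to 4% at 0.9. In a single dataset it is narrower in 80% down to 60% of cases. The result rests on an assumed ρ, a common residual variance, a common slope and arms that stay near their planned sizes. The numbers apply to the 23 laboratory endpoints only, not to the ordinal histology stages. The planned analysis is not wrong; it is less precise than the collected data allow.

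**What to change.** In SAP 6.4, for the 23 laboratory endpoints, replace the pairwise t-tests with one ANCOVA per endpoint over all three arms, with treatment and that endpoint's baseline as terms. Report each dose's adjusted difference from placebo with its 95% interval. Keep the pairwise t-test as a stated check, because it does not assume that the other dose arm shares the variance, and say whether it is pooled or Welch. Where ρ is expected to be about 0.8 or higher, a three-arm model on change without the covariate is a simpler equivalent. If the ANCOVA is also used for the four histology stages, label it approximate there. Settle the choice before unblinding.

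The cost is SAP wording and one SAS procedure, with no new data. Statistically, one df goes to the covariate, and the intervals depend on the common-variance and common-slope assumptions, which the SAP should state.

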## Appendix 2: NAFLD Activity Score

[figure not shown]
NAFLD Activity Score		
Item	Definition	Score/Code
Low- to medium-power evaluation of parenchymal involvement by steatosis		
Steatosis	<5%	0
	5% -33%	1
	>33% -66%	2
	>66%	3
Inflammation		
Lobular Inflammation	No foci	0
	<2 foci per 200 X field	1
	2-4 foci per 200 X field	2
	>4 foci per 200 X field	3
Liver cell injury		
Ballooning*	None	0
	Few balloon cells	1
	Many cells/prominent ballooning	2
*Ballooning classification: few indicates rare but definite ballooned hepatocytes as well as case that are diagnostically borderline		
Final NAFLD Activity Score = Steatosis Score + Lobular Inflammation Score + Ballooning Score		
Fibrosis Score		
Item	Definition	Score/Code
Fibrosis Stage	None	0
	Perisinusoidal or periportal	1
	Mild, zone 3, perisinusoidal	1A
	Moderate, zone3, perisinusoidal	1B
	Portal/periportal	1C
	Perisinusoidal and portal/periportal	2
	Bridging fibrosis	3
	Cirrhosis	4
Adapted from: Design and Validation of a Histological Scoring System for Non-alcoholic Fatty Liver Disease. (HEPATOLOGY, Vol. 41, No. 6, 2005 KLEINER ETAL.)		

Approved by: [name] [name]	Protocol No.: SARO.17.004.02.PROTOCOL Version No.: 2.0
------------------------------------	---

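### At 6 v 3 patients, the t interval for change in fibrosis stage can collapse to 0 (0 to 0), and its coverage is otherwise erratic; stage counts with exact intervals would avoid this

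*SAP*

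**What the plan says.** SAP section 6.4 sets the method for most secondary endpoints: "Two-sample t-test will be used to compare the treatment differences for the following endpoints", for each saroglitazar dose against placebo. One listed item is "Change from baseline in stage of fibrosis at Week 24". The same list holds the steatosis, lobular inflammation and ballooning scores and the laboratory parameters. The section adds that "treatment differences and 95% confidence for the treatment differences will be provided" and that "All p-values presented are for the descriptive purpose only". It does not say whether the variance is pooled or unequal (Satterthwaite), and it has no rule for zero variance.

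SAP section 4 plans "approximately 15 evaluable patients randomized in a 2:2:1 ratio", that is 6, 6 and 3, and states that "No formal sample size estimation was performed". Each comparison is therefore 6 v 3 at best. Under SAP section 6.8 baseline values are not carried forward, so a missing Week 24 biopsy can reduce these numbers.

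Protocol inclusion criterion 4 admits fibrosis stages 0 to 3. Appendix 2 of the protocol scores fibrosis from 0 to 4, with stage 1 divided into 1A, 1B ("Moderate, zone3, perisinusoidal") and 1C.

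**The concern.** A t interval takes its width entirely from the observed spread. Change in stage over 24 weeks is a small whole number, and many patients may show none. With nine patients the observed spread can be zero, and the interval then claims complete certainty when the data say very little. In a study without formal hypothesis tests, the intervals are what tell the reader how uncertain a result is. The label on the p-values does not extend to them. At stake is a printed fibrosis comparison whose error bars can vanish, or change a great deal when one patient moves one stage.

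**Working it through.** **Inputs.** Arm sizes 6, 6 and 3 (SAP section 4); two-sample t-test with a 95% interval, taken as two-sided (SAP section 6.4). The plan's own figure reproduces: 15 × 2/5, 15 × 2/5 and 15 × 1/5 give 6, 6 and 3. The documents give no stage-change rates, so every rate below is an assumption. Changes are limited to -1 (improved), 0 and +1 (worsened).

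**1. When the interval collapses.** The pooled half-width is t(0.975; 7 df) × s × √(1/6 + 1/3) = 2.365 × s × 0.707. If nobody changes, s = 0, the interval is 0 (0 to 0), and t and p are 0/0. The Satterthwaite form collapses too. If one drug patient improves and the other eight do not change, the pooled result is -0.17 (-0.74 to 0.41), so one patient takes the width from 0 to 1.15.

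**2. How often.** If each patient keeps the same stage with probability s, all nine do so with probability s^9:
- 0.7^9 = 4.0%
- 0.8^9 = 13.4%
- 0.9^9 = 38.7%

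**3. What the data would support.** The exact (Clopper-Pearson) upper limit for 0/n is 1 - 0.025^(1/n), which is 45.9% for 0/6 and 70.8% for 0/3. An exact unconditional, score-based interval for the difference in proportions, 0/6 v 0/3, is about -70 to +46 percentage points.

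**4. Coverage.** All outcomes at 6 v 3 were enumerated and the probability of pooled intervals containing the true mean difference was summed. With improve/same/worsen rates i, s, w (drug) and i', s', w' (placebo), the zero-width probability is (i^6 + s^6 + w^6)(i'^3 + s'^3 + w'^3).

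| Drug, improve/same/worsen (%) | Placebo (%) | True difference (stages) | Zero width | Coverage, pooled |
|---|---|---|---|---|
| 10/80/10 | 10/80/10 | 0 | 13.5% | 97.2% |
| 15/70/15 | 15/70/15 | 0 | 4.1% | 95.7% |
| 20/60/20 | 20/60/20 | 0 | 1.1% | 94.7% |
| 10/85/5 | 5/90/5 | -0.05 | 27.5% | 71.6% |
| 20/80/0 | 0/100/0 | -0.20 | 26.2% | 73.6% |
| 20/80/0 | 10/90/0 | -0.10 | 19.1% | 80.0% |
| 5/90/5 | 30/50/20 | +0.10 | 8.5% | 78.0% |

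In the fourth row, 27.5 of the 28.4 points of non-coverage are collapsed intervals; in the fifth, 26.2 of 26.4; in the sixth, 19.1 of 20.0. The last row is an exception: only 8.5 of its 22.0 points come from collapse. There the more variable arm is also the smaller, and the Satterthwaite form covers 89.8%. Where the arms are alike, a collapsed interval at 0 counts as correct because the true difference is 0. It supplies 13.4 of the 97.2 points in the first row.

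**5. Over wider ranges of assumed rates.**
- Same distribution in both arms, 40-90% unchanged (88 settings): pooled coverage is at least 94.2%, median 95.5%.
- Arms allowed to differ, three assumed ranges: pooled coverage is below 95% in 56%, 60% and 74% of settings (medians 94.7%, 94.5% and 93.1%). Satterthwaite coverage is below 95% in 21%, 37% and 51%.

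**6. Effect of the unnamed variance form.** If 4 of 6 drug patients improve by one stage and 0 of 3 placebo patients change, p is 0.068 pooled, 0.025 Satterthwaite and 0.167 by Fisher's exact test on the counts.

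**The case against.** The strongest reply is that little depends on this interval. The study is a proof of concept without formal tests, the p-values are descriptive, and fibrosis stage is one secondary comparison among many. That stands and limits the severity. It does not excuse a printed 0 (0 to 0).

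Four stronger readings are tempting, and the documents do not support them.

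- **That the interval under-covers in most plausible cases.** This depends on assumed rates and on a variance form that the SAP does not name. With alike arms, pooled coverage stays at or above about 94%. The 72% case is almost entirely the collapsed interval missing a true difference of 0.05 of a stage.
- **That the primary endpoint is compromised.** The absence of fibrosis worsening in the primary and first responder endpoints is a patient-level condition. The t interval for mean change does not enter it.
- **That the planned output cannot separate offsetting changes from no change.** One +1 and one -1 among six give a mean of 0.00, but SAP section 6.1 also prints the SD, minimum and maximum, which differ. Nor are counts of improved and worsened patients excluded. Section 6.1 tabulates categorical variables by frequency and leaves open whether stage is one of them.
- **That the 1A/1B/1C codes make the endpoint unanalysable.** Eligibility uses whole stages and SAP section 6.4 counts improvement in stages, so collapsing to stage 1 is the natural reading. One line would settle it.

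**Conclusion.** The point holds in a limited form. Followed as written, SAP section 6.4 gives an interval of zero width and no p-value for fibrosis stage whenever nobody in a 6 v 3 comparison changes stage. The probability is 4%, 13% or 39% per comparison if 70%, 80% or 90% of patients are unchanged. In other cases coverage is erratic: near or above 95% when the arms share one distribution, and down to 72-80% in some settings where few patients change and the arms differ. The collapse follows from the formula and needs no assumption. Its frequency and the coverage figures rest on assumed rates and on all nine biopsies being available. Severity is low to moderate.

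**What to change.** In SAP section 6.4:

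- Remove change in fibrosis stage from the t-test list.
- Report per arm the number and percentage improved by at least one stage, unchanged, and worsened by at least one stage, counting 1A, 1B and 1C as stage 1, with Clopper-Pearson 95% intervals.
- For each dose against placebo, give the differences in percentage improved and in percentage worsened, each with an exact unconditional 95% interval. This keeps a between-arm estimate.
- If a descriptive p-value is wanted, use Fisher's exact test, which the SAP already uses for its responder endpoints, or an exact rank-sum test.
- Keep mean change in stage as a descriptive statistic without a t-based interval.
- The steatosis, inflammation and ballooning scores can collapse in the same way. State in advance that the same counts and exact intervals replace the t interval for any of them whenever the within-arm variances in a comparison are zero.

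The cost is SAP wording and a table shell, with no new data. The downside is wider intervals and no single interval for a mean difference in stage.
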